10.4.5 Baseline Descriptive Statistics

Section Demographic and military service demographics will be presented. Appropriate statistical tests for categorical and continuous data will be calculated.

10.4.6 Sub-Group Analyses

See Section 10.4.2 (Analysis of the Primary Endpoints) for the analysis plan for each of the study aims.

10.4.7 Tabulation of individual Participant Data

Not applicable, individual participant data will not be listed by measure or time point.

11. REGULATORY, ETHICAL, AND STUDY OVERSIGHT CONSIDERATIONS

11.1 INFORMED CONSENT PROCESS

11.1.1 Consent/Accent Procedures and Documentation

During the consent appointment, potential participants will have the study explained to them in a private location in-person, by phone, or by video teleconference (using a secure video teleconferencing platform) using a paper form, mailing or emailing electronic consent documents to potential participants, or electronic consent (using online eConsent built in the UTHSCSA REDCap) on Fort Hood at the designated STRONG STAR offices in the Shoemaker Center. The potential participant will be sent a link to the eConsent and/or mailed (electronically or by post) and/or given a copy of the informed consent document (ICD) to read. After the potential participant has read the ICD, and a member of the study team has reviewed the risks and benefits of the study to ensure the participant understands the research, the participant will be given the opportunity to discuss the research with family and friends. The research team will be available to answer any questions about the research on the phone, in-person or using a HIPAA-compliant telehealth platform. Once the potential participant has reached a decision, the participant will sign the consent form either electronically or on a paper form. A copy of the ICD will be given to the participant. Additionally, as noted in the informed consent document, the Fitabase Terms of use (<https://www.fitabase.com/terms>) and the Fitabase Privacy Policy (<https://www.fitabase.com/privacy>) will be provided to the potential participant to read and review.

Following consent, participants will have the option of receiving text messages and phone calls using a study cell phone to remind them of upcoming study appointments as is usual practice by CRDAMC.

As described in the consent, participants on active duty will have the option of having their Command or employer notified by the Research Staff to ensure active duty service members and veterans are afforded the time to participate in the study. Command or employer agreement to allow for duty time to participate in this study is not a requirement for study participation.

11.1.2 Consent for minors when they reach the age of majority N/A

11.1.3 Consent of Subjects who are, or become, decisionally impaired N/A

Adults unable to provide consent are excluded from enrolling in the protocol. Adults who become decisionally impaired during study participation will be excluded from the study and the team will coordinate to refer for appropriate care.

11.2 STUDY DISCONTINUATION AND CLOSURE

Abbreviated Title: mCPT+CRP

Version Date: 07/10/25

The study may be discontinued and/or closed based on the PI decision, sponsor/funder decision, regulatory or other oversight bodies' review of serious, unexpected, and/or related AEs, noncompliance, and/or futility.

11.3 CONFIDENTIALITY AND PRIVACY

Confidentiality of Study Data: Data will be stored by an assigned participant code number so that data records can be viewed only by password-authenticated, authorized investigators and study personnel. All assessment and CRP sessions will be audio-recorded. Recordings will be labeled with the participant's study id number and will be stored in the STRONG STAR database until the end of the study. Audio recordings will be stored in the STRONG STAR Repository at the end of the study.

REDCap and/or the STRONG STAR eCAP online data capture system will be used for data collection and monitoring. The REDCap (Research Electronic Data Capture) platform is a HIPAA-secure data management system. REDCap provides audit trails for tracking data changes and maintains a secure environment for data storage, reducing the risk of data breaches. Emails and mobile phone texts will be sent to participants with a survey link, username, and password. Survey data will be transmitted to the REDCap server using an encrypted, secured link and stored at UTHSCSA on password-protected computers and secured cloud storage. The STRONG STAR password protected database is housed on a secure UTHSCSA server (physically located at the Advanced Data Center; ADC) by a member of the research team. Electronic data will be stored and managed by the STRONG STAR Data Management Core staff. If needed, the overall PI and named collaborators will have access to identifiable data as agreed to by participants through the signed HIPAA authorization through the STRONG STAR website and UTHSCSA server. All UTHSCSA STRONG STAR network connectivity is segmented with Access Control Lists and is not accessible to any other UTHSCSA network segments. The ADC has 24x7 onsite security, card key, biometric access controls and video surveillance. UTHSCSA ADC facility also maintains Gen 2 firewall devices to protect and prohibit any unauthorized physical or electronic access to UTHSCSA data. All UTHSCSA network devices are monitored by state of the art monitoring applications that include configuration audit, management, and availability 24x7. The UTHSCSA STRONG STAR data server is currently a VMware Instance running Windows Server 2016 Enterprise Standard with daily backup services and vSphere Business Continuity Advanced Failover.

EMA is administered through the HIPAA compliant MetricWire system, which provides a cross-platform (iOS and Android) application for the delivery of EMA surveys and collection of phone sensor data. EMA data will be collected over a 4-week period. Data will be identified on MetricWire using the participants identification number. Data are stored on the Metricwire cloud servers accessible only to authorized study staff. Data will be downloaded from MetricWire into an Excel or CSV file and uploaded to the study database for analysis.

Access to Study Data: Every member of the Research Team will be trained and monitored about how to handle and protect both medical and research records. Furthermore, the Research Team strictly controls access to study data. Only select STRONG STAR Data Core personnel have direct access to the data on a "need to access basis." Data Core also follows the Principals Of Least Privilege (POLP). For example (but not limited to) detecting and repairing data corruption and producing reports not currently within the STRONG STAR system. All user activity is tracked and recorded within the system so if any records are added, altered or viewed the action is recorded and can be recalled for auditing purposes. Access to this information will require a password-protected login available only to authorized STRONG STAR Data Core staff.

Research staff can enter and view data only through use of the web-based database management software interfaces. These display data only to appropriate personnel with logon privileges for delimited purposes. The database maintains a table of authorized users. Users are individually assigned a role within the application that specifies privileges for that user. Logins to data websites and databases are password

Abbreviated Title: mCPT+CRP

Version Date: 07/10/25

protected. All applications can be independently configured to perform specific tasks and utilize customer-specific security models, database connection schemes, and resources based on such roles.

Every member of the research team will be trained and supervised about how to handle and protect both medical and research records. Furthermore, the research team strictly controls access to study data.

Limits of Confidentiality: Complete confidentiality cannot be promised for military personnel because information regarding the service member's health may be required to be reported to appropriate medical or command authorities to ensure the proper execution of the military mission, including evaluation of fitness for duty. Based on the screening and testing done in the conduct of this research, the team may find out that participants are having unusual mental health symptoms, are consuming dangerous amounts of alcohol, or are feeling like hurting themselves or others. The research team will work with participants to get them the care they need. This care may result in the military revoking participant's clearances, credentials, or other privileged access or duty. Furthermore, suspected or known abuse or neglect of a child, a disabled person, or an elder or threatened violence to themselves or others must and will be reported to appropriate authorities in accordance with state law. There are other local health-reporting requirements that need to be reported.

Data from the Fitbit will be collected using Fitabase, <https://www.fitabase.com/>, a data management platform designed to support research projects using wearable and internet-connected devices. As described on the Fitabase website, <https://www.fitabase.com/resources/knowledge-base/working-with-the-irb/>, for collection of the activity data from the Fitbit, a research staff member will create a unique email and password combination in order to create an account on Fitbit.com. The following information will be entered:

- First & Last Name: A de-identified placeholder name.
- Date of Birth: The first day of the month of birth.
- Sex: The participant's biological sex.
- Height: The participant's height.
- Weight: The participant's weight.

These personal demographic details (i.e., date of birth, sex, height, and weight) are required for accurate estimation of data captured by the Fitbit Device. The Fitbit account will be connected to a research device or to the participant's own personal Fitbit if they use a Fitbit Inspire. Once the device is connected to the study-generated and study-controlled Fitbit account it will be manually connected to the Fitabase platform and assigned a unique study ID so that data will be synced and available for viewing and downloading by research staff. All data associated with the Fitbit device will be linked to the study ID in the Fitabase platform. Participants will be given the connected Fitbit device and be provided with the associated email/password so that they may login into the Fitbit.com user account, use the online Fitbit dashboard, and associated mobile applications. They will be informed that research staff will be able to access, view, and download their data through the Fitabase platform.

The research team will set up a study project within the Fitabase system for generating unique identifiers and connecting participants' Fitbit devices to the Fitabase system. When an authorized member of the research team logs into the Fitabase system they will be able to see all currently connected devices and the associated study IDs. Each study identifier has a profile that includes the Fitbit data described in the consent documents. Upon authorization by the PI or participant the Fitabase system will be granted access data gathered by the participant as they use the Fitbit device during the data collection timeframe as described in the consent documents. When the data has been downloaded to Fitabase, a member of the research team will navigate to the participant's profile and download CSV (comma separated value) files that contain sleep data to the secure lab server. No other data will be downloaded. Once the study has been completed and the data has been downloaded and scanned for errors, the participant's profile will be deleted and the authorization will be removed. The Fitabase data security and privacy practices and

Abbreviated Title: mCPT+CRP

Version Date: 07/10/25

policies are described at <https://www.fitabase.com/resources/knowledge-base/working-with-the-irb/data-security-privacy/>.

Privacy Measures. All study activities will occur in a private room or using secure telecommunication means.

Sensitive Information: UTHSCSA STRONG STAR research staff will be trained to evaluate research participants and assess risk of harm to self, others, and military mission. Sensitive information will be reported according to federal, Department of Defense, and state code regulation. Telephone-based contacts will only occur using secure telehealth platforms or landlines to ensure privacy during telephone-based assessment. Assessors will be trained in privacy practices and calls will only take place with participant consent. Calls will originate from a private room or office at CRDAMC. Procedures for telephone contact with active duty service members and veterans will comply with the provisions set forth in DoD Directive 4640.06 (which prohibits discussion of classified information on non-secure calls). Information safeguards will comply with DoD Directive 5400.11 (“DoD Privacy Program”).

This study may involve remote and/or virtual research interactions with participants by the research staff. Privacy and confidentiality are not guaranteed due to the nature of the electronic conferencing platforms that will be used, but precautions are in place to minimize the risks and participants will be informed of actions we and they can take to minimize the risk.

11.3.1 Measures Taken to Ensure Confidentiality of Data Shared per the Data Sharing Policies

The PI will ensure all mechanisms used to share data will include proper plans and safeguards for the protection of privacy, confidentiality, and security for data dissemination and reuse in accordance with the participants’ consent and HIPAA authorization. Plans for archiving and long-term preservation of the data will be implemented as appropriate.

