order each day. These procedures are in line with those currently of DoD-funded EMA research of CRP (W81XWH-22-2-0072; PI [name], Co-I [name]).

EMA is administered through the HIPAA certified MetricWire system, which provides a cross-platform (iOS and Android) application for the delivery of EMA surveys and collection of phone sensor data. EMA data will be collected for approximately a 4-week EMA period. The MetricWire system has been enhanced to comprehensively collect and analyze participant interaction data through various phone sensors, ensuring privacy and battery conservation. As part of the Intake Interview, participants will be instructed how to set up, log into, and manage their MetricWire account on their smart phone. The participant will enter their email address to activate their account. No PHI is maintained by the MetricWire. Question prompts are sent out by MetricWire and the participant's responses are linked to the participant via their study ID number which The OSU collaborators will download for analysis. All EMA prompts contain an integrated safety protocol to direct participants to their treatment team and/or emergency services should we identify suicide risk during momentary assessments. See Section 9.3 (Safety Assessments) below for details.

20. *Fitbit.* Fitbit Inspire HR will measure heart rate, physical activity, and nighttime wakefulness. Fitbit has psychometric validation for assessing each of these constructs (Wallen et al., 2016). Fitbit data will be collected through Fitabase, HIPAA-compliant software. This product collects Fitbit data (connected to an identification number) in real-time and makes it accessible to the research team for continual monitoring. Fitabase provides more fine-grained detail about the data than is typically provided through Fitbit.

21. *Qualitative Interviews.* Within 1 month of ending therapy, participants will complete one 45–60-minute semi-structured interview with study staff, which will be recorded and later transcribed for data analysis. Sample interview questions are listed below and will focus on participants' treatment experiences, strategies for coping with suicidal thoughts, and treatment acceptability.

Sample qualitative interview questions	
Treatment Experiences	What part of the treatment do you think helped you the most? How so?
	Was there a time during treatment where it “clicked” or you felt more comfortable with the materials and understanding?

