window (up to 42 EMA surveys per participant) for each participant: stability (i.e., the autocorrelation of scores over time), severity (i.e., mean score across all responses), and variability (i.e., the root mean square successive difference [RMSSD] across all responses). Each change index will be entered as an independent variable into a linear regression model predicting pre-post change in SSI score and a binary logistic regression model predicting follow-up suicidal behavior. To evaluate the specificity of these findings to the two weeks of active treatment, we will expand these analyses to include all 5 weeks of planned EMA data collection (i.e., 1 week prior to treatment start, 2 weeks of treatment, 2 weeks after treatment completion). This approach will allow us to distinguish treatment-specific patterns from more general patterns that signal treatment response and treatment relapse. **Power Analysis:** Power calculations for H3 were conducted using G*Power 3.1.9.2 (for suicidal ideation) and PROC POWER in the SAS 9.4 software (for suicide attempts). For the linear regression model, N=150 yielded 80% power to detect a medium effect ($R^2=0.06$) and for the binary logistic regression, N=150 provided >80% power to detect an odds ratio=1.5, assuming a conservative 20% of participants attempts suicide during follow-up.

Exploratory Research Question 1: Which subjective, objective, and treatment-related factors are most useful for predicting treatment response (i.e., change in severity of suicidal ideation) and treatment relapse (i.e., follow-up suicidal behavior)?

We will use the same analytic approach described for H3 but extend the analyses to all other variables assessed via EMA (i.e., positive and negative affect, negative thinking, and maladaptive behaviors) and Fitbit (i.e., physical activity, sleep quality). We will construct a series of models to determine which variables (and combination of variables) maximize the variance explained in pre-post change in SSI score and follow-up suicidal behavior. **Power Analysis:** Power calculations for RQ1 were conducted using G*Power 3.1.9.2. Assuming our model includes no more than 6 predictor variables, N=150 yielded 80% power to detect R^2 increases of 0.06-0.08 associated with each additional predictor variable.

Hypothesis 4: More frequent CRP use will be correlated with reductions in suicide attempts and suicidal ideation.

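### Section 11.3 limits the Fitbit export to sleep data, but exploratory RQ1 plans to use Fitbit physical activity as a predictor

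*Protocol*

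**What the plan says.** Four statements in the protocol bear on what happens to the Fitbit data.

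- **What is measured (Section 9.2.1, Fitbit item).** "Fitbit Inspire HR will measure heart rate, physical activity, and nighttime wakefulness".
- **Why the account exists (Section 11.3).** The Fitbit.com account is created "for collection of the activity data from the Fitbit". Participants are to be told that "research staff will be able to access, view, and download their data through the Fitabase platform".
- **What is exported (Section 11.3, next paragraph).** A team member downloads CSV "files that contain sleep data to the secure lab server. No other data will be downloaded". After study completion, and once the download has been scanned for errors, "the participant's profile will be deleted and the authorization will be removed".
- **What is analysed (Section 10.4.2, RQ1).** The approach used for Hypothesis 3 is extended to other variables from momentary assessment and from "Fitbit (i.e., physical activity, sleep quality"). The stated plan is: "We will construct a series of models to determine which variables (and combination of variables) maximize the variance explained in pre-post change in SSI score". The same is planned for suicidal behavior during follow-up.

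**The concern.** RQ1 asks which subjective, objective and treatment-related factors best predict response and relapse. The two Fitbit variables are the only device-measured predictors that the RQ1 paragraph names. The export rule admits one of them and expressly excludes the other.

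That leaves staff with two instructions that cannot both be met. If they follow Section 11.3, RQ1 is run without a planned predictor. If they export activity data to serve RQ1, they depart from a data-handling commitment in the confidentiality section, which is a deviation as Section 11.8 defines the term. A statistical analysis plan could not settle this, because it cannot authorise the export of data that the protocol says will not be downloaded.

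**Working it through.** No stated sample size, power or error rate is in question, so there is no figure of the plan's to reproduce. The check sets the sections side by side, one Fitbit variable at a time.

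| Variable | Listed as measured (9.2.1) | Named for RQ1 (10.4.2) | Exported (11.3) |
|---|---|---|---|
| Sleep (nighttime wakefulness / sleep quality) | yes | yes | yes |
| Physical activity | yes | yes | **no** |
| Heart rate | yes | no | no |

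1. **Physical activity.** It is measured, it is named for RQ1, and it is barred from export. This is the direct contradiction. It affects one of the two Fitbit predictors named for RQ1.
2. **Could the sleep files contain activity?** The protocol does not treat the two as one. Section 10.4.2 lists physical activity and sleep quality separately, and Section 9.2.1 lists physical activity apart from nighttime wakefulness.
3. **Is there another route?** None is stated. For momentary-assessment data, by contrast, Section 11.3 describes download from the survey platform and upload to the study database for analysis, with no limit by variable. Section 9.2.1 says the team can monitor Fitbit data in Fitabase, but viewing data on a platform does not give an analysable file.
4. **Heart rate.** It is measured and not exported, but no stated analysis uses it. No analysis is therefore contradicted. What remains is a listed measure with no stated purpose.
5. **Which analyses are affected?** Hypothesis 1 uses time to suicide attempt. Hypothesis 2 uses scores on the Scale for Suicide Ideation (SSI). Hypothesis 3 uses momentary ratings of suicidal ideation. Hypothesis 4 uses momentary-assessment counts of plan use. None draws on Fitbit data; only RQ1, labelled exploratory, does.
6. **Volume of data.** With the target of 150 randomized participants and 28 days of wear, the ceiling is 150 × 28 = 4,200 participant-days of activity records. At the lower payment threshold in Section 6.6.2 (5 of 7 days, so 5 × 4 = 20 days), it would be 150 × 20 = 3,000. These figures count data collected. They do not measure any effect on results.

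**The case against.** The strongest reply is that this is a drafting slip with little at stake, and that the text does not establish a loss.

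- **Section 11.3 also speaks of data being available to download.** It does, and the protocol sets no order of precedence between its sentences. But those statements describe what the platform permits and what participants are told, whereas the sleep-only sentence says what staff will do and excludes the rest. Even on the reading kindest to the plan, Section 11.3 contradicts itself and needs amendment.
- **Nothing is lost until the study ends.** This stands. A reader might infer that activity data are irretrievably destroyed. The documents do not support that: deletion follows study completion and error-checking, the data stay linked to the study ID in Fitabase until then, and nothing says that the separate study-controlled Fitbit.com account is deleted.
- **Heart rate is not an analysis variable.** This stands too. A reader might count heart rate as a second lost predictor and say that two of the three measured constructs are forfeited. RQ1 does not name heart rate, and not exporting a variable with no planned use can be ordinary data minimisation.
- **The direction of the fix is not settled.** This also stands. Section 11.3 ties the Fitbit data to what the consent documents describe, and those are not at hand. If consent covers sleep only, widening the export is not the only answer.
- **RQ1 would largely survive.** Correct: it also draws on several momentary-assessment variables whose export is provided for.

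**Conclusion.** The contradiction is real but narrow. Carried out as written, Section 11.3 leaves Fitbit physical activity, one of the two Fitbit predictors named for RQ1, out of the exported data, so RQ1 cannot be run as planned. Sleep would then be the only device-measured predictor among those the RQ1 paragraph names. Hypotheses 1 to 4, the primary outcome and their power statements are untouched.

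Severity is minor to moderate. A stronger grading might be inferred from the deletion clause, but the affected analysis is exploratory and the conflict can be corrected at any time before profiles are deleted.

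The conclusion assumes that the sleep-only sentence is meant as an operating rule and that no export route exists outside the protocol. It does not depend on what the consent says; that decides only which section has to give way.

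**What to change.** 1. Amend the export sentence in Section 11.3 so that the download covers every Fitbit variable RQ1 uses, namely physical activity and sleep, for the 28-day window.
2. Require that these files be verified as complete before any Fitabase profile is deleted or its authorization removed.
3. Confirm that the consent wording covers the same variables. If it covers sleep only, either amend the consent or remove physical activity from RQ1 in Section 10.4.2.
4. For heart rate in Section 9.2.1, either state its use and add it to the export, or stop listing it as a study measure.

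The cost is about one amended sentence in Section 11.3, a short verification step and a consent check, plus a consent amendment if that check shows a gap. No new data collection is needed, since the device data already flow to Fitabase. The change should be made before any profile is deleted.
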